### 8.2.2. Laboratory Tests

Laboratory test reference ranges will be listed (*Listing 16.2.8.1*).

Abnormal results (categorised as high, low and abnormal) will be listed for the following laboratory tests parameters.

Laboratory Test	Parameters
Hematology ( Listing 16.2.8.2.X )	Haemoglobin, Haematocrit, Platelet Count, Red Blood Cell Count, Mean Corpuscular Haemoglobin (MCH), Mean Corpuscular Haemoglobin Concentration (MCHC), Mean Corpuscular Volume (MCV), White Blood Cell Count, Neutrophils, Lymphocytes, Monocytes, Eosinophils, Basophils
Biochemistry ( Listing 16.2.8.3.X )	Alkaline phosphatase, Aspartate aminotransferase, Alanine aminotransferase, Gamma-glutamyl transpeptidase, Potassium, Sodium, Chloride, Inorganic phosphate, Glucose, Urea, Bilirubin (direct and total), Cholesterol, Triglycerides, High density

	lipoprotein-cholesterol, Low density lipoprotein-cholesterol, Protein (total), Albumin, Creatine kinase, Creatinine, Follicle-stimulating hormone (FSH)  , Human Chorionic gonadotrophin (hCG) 
Coagulation ( Listing 16.2.8.4.X )	Prothrombin time, International normalised ratio, Activated partial thromboplastin time
Urinalysis ( Listing 16.2.8.5.X )	Specific gravity, pH, Protein, Glucose, Ketones, Urobilinogen, Human chorionic gonadotropin (hCG)  , Microscopic examination 
Serology ( Listing 16.2.8.6.X )	Hepatitis B surface antigen, Hepatitis C virus antibody, Human immunodeficiency virus antigen/antibodies

 Females only; performed at Screening only

 Females only; a serum pregnancy test will be performed at Screening and a urine pregnancy test at all other time points

 Performed only if required, based on urinalysis results

Summary tables for certain laboratory test parameters may be performed upon review of data depending on the number of abnormal values observed. Baseline will be Day -1.

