10.3 Statistical analysis

10.3.1 General considerations

The statistical analysis will be performed using SAS® Version 9.2 or higher.

A SAP containing detailed data handling, analysis methods, outputs (tables, figures and listings) will be developed and approved prior to database lock. Additional analysis may be performed if deemed necessary. Any deviations from the planned analysis will be described and justified in a separate document and in the CSR.

All variables will be summarised by group and time point, if appropriate. Unless otherwise stated, continuous data will be summarised descriptively using N (number of subjects), n (number of subjects with observations), mean, standard deviation (SD), minimum, median and maximum. Categorical data will be summarised using frequency tables (frequency and percentage).

The PK parameters of MCI-186 and its metabolite in plasma will be determined from individual concentration-time data by non-compartmental analysis methods using Phoenix® WinNonlin® ver.6.3 or higher.

All individual subject data will be listed.

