10.3.5.2 Safety endpoints

The objective of the evaluation is to investigate safety and tolerability of MCI-186. All safety and tolerability variables will be listed and summarised descriptively. There will be no formal statistical analysis of the safety data. In general, safety data will be summarised by group and day, as appropriate.

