10.3.5.5 Routine safety laboratory tests

Laboratory variables and changes in laboratory variables from baseline will be summarised (N, n, mean, SD, median, minimum and maximum) at each time point. Baseline will be Day -1.

Urinalysis variables will be listed by subject and time point.

Values outside the normal ranges (provided with the laboratory report), will be flagged in the subject data listings.

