## 1. INTRODUCTION

This statistical analysis plan (SAP) is based on the final protocol (v3.0) dated 06-FEB-2019. The plan covers statistical analysis, tabulations and listings of the study data to investigate the pharmacokinetics of MCI-186 in subjects with severe hepatic impairment compared to subjects with normal hepatic function.

Any statistical analysis details described in this document supersede any description of statistical analysis in the protocol.

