#### Pharmacokinetic parameters of MCI-186:

- $t_{1/2}$
- Time to reach peak concentration ( $t_{max}$ )
- Terminal elimination rate constant ( $\lambda_z$ )
- Total clearance (CL)
- Volume of distribution at steady state ( $V_{ss}$ )
- Volume of distribution during the terminal phase ( $V_z$ )

- Mean residence time (MRT)
- Unbound area under the concentration-time curve from time zero to infinity (AUC0-∞)
- Unbound total clearance (CLu)

Pharmacokinetic parameters of the sulfate conjugate:

- Cmax
- AUC0-last
- AUC0-∞
- t1/2
- tmax

Safety and Tolerability

- Incidence of adverse events (AEs) and serious adverse events (SAEs)
- Physical examination
- Vital signs (blood pressure, pulse rate and body temperature)
- 12-lead electrocardiogram (ECG) parameters
- Laboratory assessments including biochemistry, haematology, coagulation and urinalysis
- Columbia-Suicide Severity Rating Scale (C-SSRS; see Appendix 1 in Section 14 of the Protocol)

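### SAP 8.2.2 makes the protocol's required laboratory change-from-baseline summaries optional and dependent on the data seen, while SAP section 10 declares no change from the protocol

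*SAP*

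**What the plan says.** Protocol 10.3.5.5 is unconditional: "Laboratory variables and changes in laboratory variables from baseline will be summarised (N, n, mean, SD, median, minimum and maximum) at each time point". It fixes Day -1 as baseline, limits urinalysis to listings, and says that values outside the normal range "will be flagged in the subject data listings". Protocol 10.3.5.2 sets the general rule: "All safety and tolerability variables will be listed and summarised descriptively". Protocol 10.3.1 adds: "All individual subject data will be listed".

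SAP 8.2.2 commits to two things, a listing of reference ranges and a listing of abnormal results: "Abnormal results (categorised as high, low and abnormal) will be listed for the following laboratory tests parameters". On summaries it says only: "Summary tables for certain laboratory test parameters may be performed upon review of data depending on the number of abnormal values observed". It names Day -1 as baseline, but gives no laboratory summary table number and does not mention change from baseline.

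SAP 9.3 shows Screening, Day -1, Day 2 and Day 3 for laboratory tests. It keeps follow-up visits out of by-visit summary tables and leaves them to the listings. SAP section 10 reports no changes to the protocol's analysis. SAP section 1 gives the SAP precedence: "Any statistical analysis details described in this document supersede any description of statistical analysis in the protocol".

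**The concern.** Laboratory safety is a named secondary endpoint in SAP 2.2.2: "Laboratory assessments including biochemistry, haematology, coagulation and urinalysis". Protocol 8.5 explains why a reference-range view is not enough here. In subjects with hepatic disease, results may lie outside the healthy range because of the disease, so the protocol singles out change from baseline as an important signal for that group. SAP 8.2.2 makes that measure optional and ties it to a count of abnormal values. It names neither the parameters nor a threshold, and the decision comes after the data have been reviewed.

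A team that follows the SAP to the letter could report the study with no group-level summary of laboratory change after dosing. A reader of SAP section 10 would not know that the protocol had promised one.

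**Working it through.** Neither document gives a figure to reproduce. The check sets the two texts side by side and counts what is committed.

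**1. Obligation against option.** Protocol 10.3.5.5 says the summaries will be made. SAP 8.2.2 says they may be made, for certain parameters, after data review. SAP section 1 makes the SAP wording the operative one, so the protocol sentence does not secure the tables.

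**2. Parameters with a committed summary table.** Counted from SAP 8.2.2 to 8.2.4, taking direct and total bilirubin separately and leaving out FSH and hCG:
- Haematology 13, biochemistry 20, coagulation 3: 13 + 20 + 3 = 36 parameters, of which 0 have a committed table.
- Vital signs 4 and ECG 6: 4 + 6 = 10 parameters, of which 10 have committed tables of values and changes (Tables 14.3.2.1 and 14.3.3.1).

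Urinalysis is left out because the protocol itself only lists it.

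**3. Visits.** Protocol Table 9 plans 5 samples each for haematology, biochemistry and coagulation. This matches Screening, Day -1, Day 2, Day 3 and Follow-up; Protocol 5.2.3 confirms that laboratory tests, vital signs and ECG are all done at Follow-up. SAP 9.3 displays 4 laboratory visits, so 5 - 4 = 1 is left out. Post-dose visits with a summarised laboratory change are:
- under the protocol: 3 (Day 2, Day 3, Follow-up);
- under the SAP if the optional tables are made: at most 3 - 1 = 2;
- under the SAP if they are not made: 0.

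Protocol 10.3.5.4 applies the same time-point rule to vital signs and ECG, so their tables also fall short by the Follow-up visit.

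**4. Does the trigger track the quantity the protocol wants?** Two cases show that it does not.
- A value that is out of range at Day -1 and moves further out after dosing is counted as abnormal at both visits. The count does not register the movement.
- A value that moves after dosing but stays within range adds nothing to the count. If a parameter has few abnormal values, its table may never be made, even if a whole group shifted in one direction.

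**5. Internal signs.** SAP 8.2.2 sets a laboratory baseline and SAP 9.3 has a laboratory column. Both suggest that by-visit laboratory tables were expected. They define a baseline and a display for tables if made; they do not commit anyone to making them.

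**6. Declaration.** Steps 1 and 3 are departures from Protocol 10.3.5.4 and 10.3.5.5. Protocol 10.3.1 requires departures from the planned analysis to be described and justified. SAP section 10 records none.

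**The case against.** The strongest reply is that the protocol leaves the choice of outputs partly to the SAP. Protocol 10.3.1 assigns tables, figures and listings to the SAP and qualifies summaries by group and time point with an appropriateness clause; the synopsis and 10.3.5.2 carry similar qualifiers. This has some force for layout and grouping. It does not cancel 10.3.5.5, which is specific to laboratory data and carries no qualifier. SAP precedence settles which text operates, but it does not make section 10 true.

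A second reply is that little is lost. There is no formal testing of safety data, so choosing tables after seeing data cannot affect error control. Investigators assess all laboratory results, and clinically significant abnormalities become adverse events, which are listed and summarised. eGFR is listed. With about 6 subjects per group and one dose, individual listings carry much of the information. All of this stands and limits the weight of the point. The Follow-up omission in particular is minor for vital signs and ECG, because SAP 8.2.3 and 8.2.4 list all their data.

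A reader might also infer that the trigger is defective because severe liver disease alone would set it off. The documents do not support that as a harm. More abnormal values make the tables more likely, which is what the protocol wants. The Child-Pugh entry score involves only albumin, bilirubin and prothrombin time, 3 of the 36 parameters, and its points are not shown to equal flags against laboratory reference ranges, which neither document gives. The gap lies with parameters that have few abnormal values.

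**Conclusion.** The point holds as a conflict between protocol and SAP, and it should be fixed. A required summary of a secondary safety endpoint has become optional, with 0 of 36 parameters committed. The condition for producing it does not measure change after dosing. One of three post-dose laboratory visits is left out of the by-visit tables in any case, and the statement in SAP section 10 is inaccurate.

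The effect is confined to group-level safety reporting. The primary pharmacokinetic comparison and adverse event reporting are untouched. The tables may still be produced; what is missing is the commitment.

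A reader might go further and conclude that within-range laboratory values will not be listed at all. That is not established. SAP 8.2.2 names only abnormal results, but SAP 9.3 refers to data listings that include follow-up and unscheduled visits, and Protocol 10.3.1 and 10.3.5.2 call for full listings. This is an ambiguity to clear up, not a shown omission.

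The conclusion rests on the wording of the two documents and on the counting rules stated in the check. Counting bilirubin once or including the two hormones would change the 36 but not the 0.

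**What to change.** - **SAP 8.2.2:** delete the sentence that makes laboratory tables optional. Commit to descriptive summaries by group of haematology, biochemistry and coagulation values, and of changes from Day -1, at Day 2, Day 3 and Follow-up, with table numbers. State that all laboratory values are listed and out-of-range results flagged.
- **SAP 9.3:** add Follow-up to the by-visit tables for laboratory tests, vital signs and ECG.
- **SAP section 10:** correct the statement. If any reduction is kept, declare and justify it there.

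The cost is SAP wording and a few extra descriptive tables from data already collected. No new visit, sample or test is needed. With about 6 subjects per group, the mean changes should be read as descriptive only.

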### 8.2.3. Vital Signs

Absolute values and changes from baseline will be summarized (*Table 14.3.2.1*) and shift table of clinically relevant categories will be presented (*Table 14.3.2.2*) for the following parameters.

- Systolic Blood Pressure (mmHg)
- Diastolic Blood Pressure (mmHg)
- Pulse Rate (bpm)
- Body Temperature (°C)

Baseline will be Day 1 pre-dose.

All data will be listed (*Listing 16.2.9.1*).

### 8.2.4. 12-Lead ECGs

Absolute values and changes from baseline will be summarized (*Table 14.3.3.1*) and shift table of clinically relevant categories will be presented (*Table 14.3.3.2*) for the following parameters.

- Heart Rate (bpm)
- PR (msec)
- RR (msec)
- QRS (msec)
- QT (msec)
- QTcF (msec)

The frequency counts and percentages of subjects with 12-lead ECG values outside pre-defined limit will be summarized (*Table 14.3.3.3*).

Baseline will be Day 1 pre-dose.

All data will be listed (*Listing 16.2.9.2*).

### **8.2.5. Columbia-Suicide Severity Rating Scale (C-SSRS)**

C-SSRS data will be listed (*Listing 16.2.9.3*).

### **8.2.6. Estimated Glomerular Filtration Rate (eGFR)**

eGFR data will be listed (*Listing 16.2.9.4*).

### **8.2.7. Physical Examinations**

Physical examination body systems examined at Screening, Day -1 and Day 3 will be the following:

- Abdominal
- Cardiovascular
- Gastrointestinal
- General appearance
- Eyes, Ears, Nose and Throat
- Head and Neck
- Hepatic
- Lymph Nodes
- Musculoskeletal
- Neurological
- Dermatological
- Respiratory
- Other

Abbreviated physical Examination body systems examined at all other visits.

All data will be listed (*Listing 16.2.9.5*).

## **8.3. Pharmacokinetics Evaluation**

### **8.4.1 Plasma Concentration**

All measured plasma concentrations will be listed (*Listing 16.2.6.1* and *Listing 16.2.6.2*).

All measured protein binding rate and free fraction will be listed (*Listing 16.2.6.3*)

Plasma concentrations will be summarized at each scheduled sampling time point by each group (Groups 1 and 2) (*Table 14.2.1.1* and *Table 14.2.1.2*).

Protein binding rate and free fraction will be summarized by each group (Group 1 and 2). (*Table 14.2.2*)

To visualize the concentration-time profiles of each group, the following plots will be produced in linear and semi-logarithmic scales:

1. Individual subject concentration-time plot for each group (Groups 1 and 2) overlaid in one graph (*Figure 14.2.4.1*, *Figure 14.2.4.2*, *Figure 14.2.5.1* and *Figure 14.2.5.2*).
2. Mean concentration-time plot for each group (Groups 1 and 2) overlaid in one graph

(Figure 14.2.1.1, Figure 14.2.1.2, Figure 14.2.2.1 and Figure 14.2.2.2).

In the summary tables, arithmetic mean, SD, minimum, median, maximum and geometric mean will be presented with the number of significant digits which individual concentrations are reported. In addition, CV%, and geometric CV% will be presented with 1 decimal place.

#### 8.4.2 Pharmacokinetic Parameters

The pharmacokinetic parameters listed in Section 2.2 will be calculated for each subject on active dose using non-compartmental model. All PK parameters will be listed (*Listing 16.2.6.4* and *Listing 16.2.6.5*).

The PK parameters will be summarized by each group (Groups 1 and 2). The following descriptive statistics will be calculated: N (number of subjects), n (number of valid observations), arithmetic mean, SD, CV%, minimum, median, maximum, geometric mean and geometric CV% (*Table 14.2.3.1* and *Table 14.2.3.2*).

For the descriptive statistics, the minimum and maximum will be presented according to following requirement:

- $t_{max}$ : will be presented with 2 decimal places.
- $C_{max}$ : will be presented with the number of significant digits they are reported with.
- Number of  $\lambda z$  points: will be presented with integer.
- Other PK parameters: will be presented with a fixed number of decimal places for each parameter. The number of decimal places is 2 decimal places corresponding to having 3 significant digits at the minimum by analyte.

Mean, SD, median and geometric mean will be presented with the number of decimals as follows.

- $C_{max}$ : will be presented with 4 significant digits.
- Other PK parameters: will be presented with 2 decimal places.

CV% and geometric CV% will be presented with 1 decimal place.

To visualize the relationship between measures of hepatic function and between the PK parameters of MCI-186 and the sulfate conjugate, the following scatter plots of  $AUC_{0-last}$ ,  $AUC_{0-\infty}$ ,  $AUC_{u0-\infty}$  and  $C_{max}$  (on the vertical axis) versus Child-Pugh score, Child-Pugh classification (Normal, Severe), albumin, bilirubin, prothrombin and eGFR (on the horizontal axis) with regression line, will be produced in linear scales:

The PK parameters of ( $AUC_{0-last}$ ,  $AUC_{0-\infty}$ ,  $AUC_{u0-\infty}$  and  $C_{max}$  of MCI-186 and the sulfate conjugate) vs (Child-Pugh score (*Figure 14.2.3.1.1* and *Figure 14.2.3.2.1*), Child-Pugh classification (*Figure 14.2.3.1.2* and *Figure 14.2.3.2.2*), albumin (*Figure 14.2.3.1.3* and *Figure*

14.2.3.2.3), bilirubin (Figure 14.2.3.1.4 and Figure 14.2.3.2.4), prothrombin time (Figure 14.2.3.1.5 and Figure 14.2.3.2.5) and eGFR (Figure 14.2.3.1.6 and Figure 14.2.3.2.6) plot will be produced for all subjects overlaid in one graph.

Following log-transformation,  $C_{max}$ ,  $AUC_{0-last}$  and  $AUC_{0-\infty}$  of MCI-186 and the sulfate conjugate will be separately analysed using a mixed effects model with treatment as a fixed effect. Example SAS code:

```
proc mixed;  
  class subject treatment;  
  model log(endpoint) = treatment / solution ddfm=kr outpm=pred;  
  lsmeans treatment / diff cl alpha=0.1;  
  run;
```

The point estimates and their corresponding 90% CIs on the log scale will then be back-transformed to provide point estimates and 90% CIs for the ratios of severe hepatic impairment / normal hepatic function (Table 14.2.4.1 and Table 14.2.4.2).

## 9. DATA PRESENTATION CONVENTIONS

### 9.1. Number of Digits to Report

#### (1) Non-PK related

Statistic	Specification	Apply to
Minimum, Maximum	Same number of DPs as the data provided in the datasets	All original (i.e. non-derived)
	see section 7.3	All derived data
Mean, Median, SD, SE, Confidence intervals	One more DP than above	All
Percentages *1	1 DP	All
Ratios	3 DPs	All
p-values *2	3 DPs	All

\*1 Percentages: use 1 DP, except for the following cases:

If the percentage is equal to 0, then leave blank, do not use (0)

If the percentage is equal to 100, then use "(100)" without a decimal

\*2 p-values: use 3 DP, except for the following cases:

If the p-value is less than 0.01, then use p<0.01

## 9.2. Treatments to Report

Treatment	For TFLs
MCI-186 30 mg / 100 mL Severe Hepatic Impairment	MCI-186 30 mg / 100 mL Severe
MCI-186 30 mg / 100 mL Normal Hepatic Function	MCI-186 30 mg / 100 mL Normal

## 9.3. Analysis Visits to Report

### (1) Non-PK related

Safety:

Analysis Visit	Apply to		
	Laboratory Tests	Vital Signs	12-Lead ECGs
Screening	X	X	X
Day -1 / Baseline	X	X	X
Day 1 / Baseline		X	X
Day 2	X	X	X
Day 3	X	X	X

Unscheduled visits, retests (same visit number assigned) and follow-up visits will not be displayed in by-visit summary tables, but will be included in the data listings.

## 10. CHANGE FROM THE PROTOCOL

There are currently no changes to the analysis from the protocol.

## 11. SOFTWARE

All statistical analyses will be performed using SAS® version 9.3 or higher.

The PK parameters will be calculated using WinNonlin® software (version 6.3 or later).

## **Appendix 1      Pharmacokinetic Parameter Calculations**

- Actual blood sampling times will be used in the calculation of pharmacokinetic parameters
- All concentrations below the LLOQ will be set at zero for pharmacokinetic calculations
- When  $k_{el}$  is missing (or cannot be determined),  $t_{1/2}$ ,  $AUC_{0-\infty}$ ,  $AUC\%_{ex}$ ,  $CL/F$ ,  $MRT$ ,  $V_z/F$  and  $V_{ss}/F$  will not be calculated.

PK Parameter Calculations		
Parameters	Unit	Calculation
$C_{\max}$	ng/mL	will be determined by visual inspection
$AUC_{0-\infty}$	ng·h/mL	$AUC_{0-\infty} = AUC_{0-\text{last}} + C_{\text{last}} / k_{\text{el}}$ $C_{\text{last}}$ : last measurable concentration
$AUC\%_{\text{ex}}$	%	$AUC\%_{\text{ex}} = (AUC_{0-\infty} - AUC_{0-\text{last}}) / AUC_{0-\infty} \times 100$
$AUC_{0-\text{last}}$	ng·h/mL	will be calculated using the linear trapezoidal method and actual times $AUC_{0-\text{last}} = \sum_{i=1}^n \frac{t_i - t_{i+1}}{2} (C_{i-1} + C_i)$
$t_{\max}$	h	Measured time of $C_{\max}$
$t_{1/2}$	h	$t_{1/2}$ will be determined as: $t_{1/2} = \log_e (2) / k_{\text{el}}$
$k_{\text{el}}$	/h	
The exponential rate constant of the terminal phase, <math>k_{\text{el}}</math>, will be estimated by log-linear regression, if determinable. The number of data points included in the regression will be determined by visual inspection. Wherever possible, a minimum of 3 data points will be used in the estimation of <math>k_{\text{el}}</math>.
 
During the analysis, this calculation method repeats regressions using the last three points with non-zero concentrations, then the last four points, last five, etc. The time of maximum concentration (<math>t_{\max}</math>) will be excluded from the estimation of <math>k_{\text{el}}</math>.
 
Points with a value of zero for the dependent variable are excluded. For each regression, an adjusted <math>R^2</math> is computed
 $\text{Adjusted } R^2 = 1 - \frac{(1 - R^2) \times (n - 1)}{(n - 2)}$ 
where <math>n</math> is the number of data points in the regression and <math>R^2</math> is the square of the correlation coefficient.
 
The regression with the largest adjusted <math>R^2</math> is selected to estimate <math>k_{\text{el}}</math>, with these caveats:
 
 
- If the adjusted <math>R^2</math> does not improve, but is within 0.0001 of the largest adjusted <math>R^2</math> value, the regression with the larger number of points is used.
 
- <math>k_{\text{el}}</math> must be positive, and calculated from at least three data points.
 

CL/F	L/h	$CL/F = Dose / AUC_{0-\infty}$
MRT	/h	$MRT = AUMC_{0-\infty} / AUC_{0-\infty}$ AUMC 0-∞ : area under the first moment curve extrapolated to infinity

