7.1.1 Compliance

IMP will be administered by the Investigator or designee. The prescribed dosage, timing and mode of administration of IMP may not be changed. Any departures from the intended regimen must be recorded in the eCRF.

IMP accountability and subject compliance will be documented throughout the study period using study-specific IMP dispensing forms. The Investigator, or suitably qualified site personnel, will supervise/oversee the administration of IMP and the exact time of dosing will be recorded in the eCRF.

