### 3. STUDY DESIGN

#### 3.1. Study Design

This is a Phase I, open-label, single-dose study to evaluate the pharmacokinetics of MCI-186 in male and female subjects with severe hepatic impairment (Group 1, n = 6), defined using the Child-Pugh classification, and in male and female subjects with normal hepatic function (Group 2, n = 6). Subjects may be replaced or additional subjects may be enrolled to ensure a minimum threshold of 6 completing subjects per group.

- Group 1: Subjects with severe hepatic impairment (Child-Pugh total score of 10 to 14 [Grade C])
- Group 2: Healthy subjects with normal hepatic function to match Group 1 for age, body weight and gender

All subjects will be administered 30 mg MCI-186 over 60 minutes on the morning of Day 1. An infusion time window of ±3 minutes is permitted.

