**Table 1 Time and events schedule**

Study Period	Screening			Treatment Hospitalisation			Follow-up		
	-21 to -2	-1	1	2	3	7 (+2)			
Time point									
Informed consent	X								
Confinement									
Outpatient	X								
Inclusion/exclusion criteria	X	X	X						
Demography & medical history	X								
Physical examination	X	X	X 				X 	X	X 
Weight	X	X					X	X	X
Height	X								
BMI	X	X							
Vital signs	X	X	X				X	X	X
12-lead ECG	X	X	X				X	X	X
Urine drugs of abuse & breath alcohol test	X	X							
Biochemistry, haematology, coagulation & urinalysis	X	X					X	X	X
C-SSRS		X					X		

Study Period	Screening		Treatment Hospitalisation						Follow-up		
	Study Day	-21 to -2	-1	1			2			3	7 (+2)
Time point											
Hepatic impairment assessment (Child-Pugh classification; Group 1 only)				■	■	■	■	■	■	■	■
eGFR	X	X								X	X
Hepatitis B & C and HIV	X	X								X	X
Pregnancy test in females	X	X								X	
Protein binding blood sampling		X									
IMP administration				←		→					
PK sampling (blood) 			■	■	■	■	■	■			
AE and concomitant medications			←								↑

Abbreviations: AE=adverse event; BMI=body mass index; C-SSRS=Columbia-Suicide Severity Rating Scale; ECG=electrocardiogram; eGFR=estimated glomerular filtration rate; HIV=human immunodeficiency virus; IMP=Investigational Medicinal Product; PK=pharmacokinetic.

- IMP administration starting time. IMP will be administered over 60 minutes. The permitted infusion time window is  $\pm 3$  minutes
- Abbreviated physical examination only
- The time windows for PK sampling during the study are as follows. All times relate to the infusion start time:
  - pre-dose: -60 to -30 minutes
  - $\pm 5$  minutes
  - +3 minutes from end of infusion
  - $\pm 5$  minutes

- [REDACTED] ±15 minutes

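### SAP Appendix 1 defines MRT without an infusion term, so for the 60-minute infusion the written formula overstates mean residence time by about 0.5 h

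*SAP*

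**What the plan says.** SAP Appendix 1 gives the MRT calculation in a row that begins "MRT = AUMC_{0-\infty} / AUC_{0". It describes AUMC only as the first-moment area extrapolated to infinity. There is no infusion term. The unit in that row is /h, whereas the SAP list of PK parameters gives h.

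The regimen is an infusion. SAP 3.1 states: "All subjects will be administered 30 mg MCI-186 over 60 minutes on the morning of Day 1", with a window of ±3 minutes. The time origin is the start of that infusion (Table 1, footnote 3: "All times relate to the infusion start time"). Appendix 1 adds: "Actual blood sampling times will be used in the calculation of pharmacokinetic parameters".

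MRT of MCI-186 is a secondary endpoint (protocol 2.2.2; SAP 2.2.2). SAP 8.4.2 lists it by subject and summarises it by group: "The PK parameters will be summarized by each group (Groups 1 and 2)". The model-based ratio and 90% CI in the same section cover Cmax, AUC0-last and AUC0-∞ only.

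On how the calculation is run, SAP 8.4.2 says only that it is non-compartmental, and SAP 11 names only the software and its version. The protocol gives no MRT formula. SAP section 1 says the SAP supersedes the protocol on analysis details, so Appendix 1 is the governing definition.

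**The concern.** AUMC/AUC is the drug's mean residence time only when the whole dose enters at time zero. When it enters at a constant rate over an hour, the average molecule arrives half an hour after the clock starts, and that half hour is counted as residence. The written formula therefore returns mean input time plus residence time, although the endpoint is named mean residence time.

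What is at stake is a descriptive secondary endpoint. No formal comparison of MRT is planned, but the study's purpose is to compare severe hepatic impairment with normal function, and the two group summaries will be read against each other. A common 0.5 h added to both makes any relative prolongation in the impaired group look smaller than it is. Vss would carry the same error if it is computed as CL × this MRT.

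**Working it through.** The documents state no MRT value, so there is no figure to reproduce. The check is an identity plus illustrations of its size.

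**Inputs**
- Infusion time T = 60 min = 1 h, window 57 to 63 min, i.e. 0.95 to 1.05 h (SAP 3.1).
- Time zero = start of infusion (SAP Table 1, footnote 3).
- Protocol Table 2 (0.5 mg/kg over 30 min, means, N = 5 per group). Adults: half-lives 0.27 and 2.27 h, Cmax 888 ng/mL, AUC0-∞ 742 ng·h/mL. Elderly: 0.17 and 1.84 h, 1041 ng/mL, 725 ng·h/mL.
- Protocol Table 1 half-lives, and the simulated Cmax of 470 ng/mL and AUC of 600 ng·h/mL for 30 mg (protocol 1.5).

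**Identity.** With linear disposition, the concentration curve from a constant-rate infusion is the bolus curve convolved with a uniform input on (0, T). Means add under convolution:

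AUMC/AUC = MRT + T/2.

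The excess is 0.95/2 = 0.475 h, 1/2 = 0.500 h and 1.05/2 = 0.525 h at 57, 60 and 63 minutes. Numerical integration of two-phase and three-phase profiles gave these same three values, whatever the shape of the profile.

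**Size on Table 2 (two phases).** Let w be the share of AUC in the fast phase and λ = ln 2 / half-life. At the end of a 0.5 h infusion,

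Cmax = (AUC/0.5) × [w(1 − e^(−0.5λ₁)) + (1 − w)(1 − e^(−0.5λ₂))], and MRT = w/λ₁ + (1 − w)/λ₂.

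- Adults: 888/1484 = 0.598 = 0.723w + 0.142(1 − w), so w = 0.786. MRT = 0.786 × 0.390 + 0.214 × 3.275 = 1.008 h.
- Elderly: 1041/1450 = 0.718 = 0.870w + 0.172(1 − w), so w = 0.782. MRT = 0.782 × 0.245 + 0.218 × 2.655 = 0.769 h.

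| | MRT (h) | Appendix 1 formula at T = 1 h | Excess |
|---|---|---|---|
| Adults | 1.008 | 1.508 | 0.5/1.008 = 50% |
| Elderly | 0.769 | 1.269 | 0.5/0.769 = 65% |

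**Size with a third, slow phase.** Using the 1.0 mg/kg half-lives in Table 1 (0.17, 0.85 and 4.50 h), scaled to Cmax 470 and AUC 600, and assuming 5% to 20% of AUC in the slow phase:
- 5%: 0.92 h becomes 1.42 h (+54%).
- 20%: 1.57 h becomes 2.07 h (+32%).

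Fits to the 40-minute regimens at 1.0 mg/kg and above, over every admissible slow-phase share and treating AUC0-24 as AUC to infinity, give MRT from 0.60 to 2.65 h. On those, 0.5 h is 19% to 84%. The ends are boundary cases. The 3-hour regimen is left out because its near-plateau end value barely identifies the phases.

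**Effect on a group comparison.** If the true ratio is R and the reference MRT is M, the apparent ratio is (R·M + 0.5)/(M + 0.5). R is assumed; the documents give no value.
- R = 2: 2.516/1.508 = 1.67 (M = 1.008); 2.038/1.269 = 1.61 (M = 0.769).
- R = 1.5: 2.012/1.508 = 1.33; 1.654/1.269 = 1.30.

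If impaired subjects' MRT were 1.5 to 3 times the Table 2 values (assumption), their own overstatement would run from 0.5/(3 × 1.008) = 17% to 0.5/(1.5 × 0.769) = 43%.

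**Vss, conditional.** CL = 30 mg / 600 ng·h/mL = 50 L/h. If Vss = CL × the uncorrected MRT, it is 50 × 0.5 = 25 L too high.

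**The case against.** The identity and the arithmetic are not in dispute. The case for treating this as minor has four parts.

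1. The available text of Appendix 1 stops at the MRT row. The Vz and Vss rows and any table notes are not visible, and an infusion term could sit there. This stands as a limit: the finding covers the text as available, and the Vss effect is only conditional.

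2. No reported value is shown to be wrong. SAP 11 says: "The PK parameters will be calculated using WinNonlin® software (version 6.3 or later)". It gives no dosing setting, and the run might apply an infusion correction. This also stands as a limit, but it does not rescue the formula. If the run follows Appendix 1, MRT is about 0.5 h too long. If the software corrects for infusion, the reported MRT will not match the prespecified definition.

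3. The consequence is small. MRT is one of nine secondary MCI-186 parameters, no ratio or CI is planned for it, and a common offset cancels in an absolute difference. All true, and the reason this is not graded higher. Each group's level is still overstated, and any relative comparison is attenuated.

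4. The percentages are soft. Table 2 comes from another regimen and has no third phase. With sampling to 48 h, a slow phase may be captured, which lengthens MRT and lowers the percentage. The 19% and 84% ends each set a reported phase to zero. This is fair: the percentages are illustrations. The 0.475 to 0.525 h offset depends on none of them.

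**Conclusion.** The concern holds. As written, Appendix 1 gives an MRT that is 0.5 h too long at 60 minutes (0.475 to 0.525 h within the window), in both groups. This rests on a constant infusion rate, the stated time origin and linear disposition, which protocol 1.5 describes as almost linear.

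In relative terms the excess is about 50% to 65% on the two-phase Table 2 fits and 32% to 54% on three-phase profiles with an assumed slow-phase share of 5% to 20%. It shrinks as true MRT lengthens. It should be fixed before database lock, because it misdefines a named secondary endpoint. The primary endpoints and CL do not use MRT and are unaffected.

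**What to change.** In SAP Appendix 1:
- Write MRT = AUMC0-∞/AUC0-∞ − T_inf/2, where T_inf is the subject's actual infusion duration, with unit h to agree with the PK parameter list.
- State that the WinNonlin run uses the IV-infusion setting, and that any MRT used for Vss is this corrected value.
- Optionally, remove /F from CL, Vz and Vss, since the endpoints are named without it and the drug is given intravenously.

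The cost is SAP wording only. Protocol 7.1.1 requires that "the exact time of dosing will be recorded in the eCRF" and that departures from the regimen be recorded, but it does not expressly require the infusion stop time. Where no stop time was recorded, use the nominal 60 minutes. Within the ±3 minute window this leaves at most 0.05/2 = 0.025 h of error: 0.025/1.008 = 2.5% and 0.025/0.769 = 3.2% of the Table 2 MRTs.
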